### **5.8. Pharmacodynamic Set**

Not applicable for this SAP.

### **5.9. Other Analysis Sets**

Not applicable for this SAP.

### **5.10. Protocol Deviations**

Protocol deviations identified by the site or the study monitor should be reported to the IRB according to the IRB’s reporting guidelines. All deviations will be recorded in the MediData Rave database and will be categorized in accord with AveXis Standard Operating Procedures

(SOP)s. Protocol deviations will be reviewed on a regular basis by the appropriate study team members throughout the course of the study.

Final

## 6. GENERAL ASPECTS FOR STATISTICAL ANALYSIS

### 6.1. General Methods

In general, descriptive statistical methods will be used to summarize the data from this study. Hypothesis testing will be performed for the efficacy endpoints based upon the predetermined sample sizes. Unless stated otherwise, the term “descriptive statistics” refers to number of patients (n), mean, median, standard deviation, minimum, and maximum for continuous data and frequencies and percentages for categorical data. Unless noted otherwise, the data will be sorted first by dose (Dose A, then Dose B, then Dose C), age group, patient number, and then by date within each patient number.

Unless noted otherwise, all safety tables will be summarized using the SS, by the actual dose received and by age group.

All descriptive statistics of efficacy tables will be summarized by the assigned dose and age group. The efficacy analyses will be performed to compare with the efficacy endpoints of patients assigned to AVXS-101 and patients drawn from a widely (peer-reviewed) published natural history dataset collected by the PNCR network; comparisons to the PNCR data will be conducted for Dose B only. Efficacy data for Dose A and Dose C will only be summarized descriptively and will not be compared to the PNCR data.

Efficacy analyses will be conducted on the ITT or ECAS as specified within each section, with analyses on the ECAS produced only if the ECAS contains a subset of patients of the ITT. Since the FAS and the ITT Set include the same patients (SAP Section 5.3), the ITT Set is used to represent the efficacy analyses by the FAS stated in the protocol.

Unless specified otherwise, all statistical testing and confidence intervals (CI) will be 2-sided and will be performed using an alpha level of 0.05. No adjustments for multiple comparisons will be made.

All statistical analyses will be conducted with the SAS® software package version 9.4 or higher.

### 6.2. Key Definitions

#### 6.2.1. Baseline Values

Unless otherwise specified, the baseline values of safety parameters and efficacy parameters of the patients enrolled in the study are defined as the last non-missing measurement or assessment prior to the dose of study medication. If multiple measurements are recorded on the same day, the last measurement recorded prior to the dose of study medication will be used as the baseline value. If these multiple measurements occur at the same time or time is not available, then the average of these measurements (for continuous data) or the worst among these measurements (for categorical data) will be considered as the baseline value.

For patients  $\geq$  6 months and  $<$  24 months at time of dosing who continue in study past 24 months of age, the score and change from baseline of HFMSE will also be the calculated. The baseline HFMSE will be defined as the patients’ first measurement of HFMSE after passing 24 months of age.

The baseline values of parameters of patients from the PNCR are defined as those captured for the study-defined baseline visit. In cases where the baseline visit HFMSE assessment was not completed, the baseline value will be defined as the first non-missing assessment.

#### **6.2.2. Study Day**

For patients enrolled in the study, the only dose of study medication will be administered on study day 1. The study day for an event occurring on or after the dose date is defined as event date – dose date + 1. The study day for an event occurring prior to the dose date is defined as event date – dose date.

For patients from the PNCR dataset, the date of baseline assessment for the primary endpoint will be considered study day 1. The study day for an event occurring on or after the date of enrollment is defined as event date – enrollment date + 1. The study day for an event occurring prior to the date of enrollment is defined as event date – enrollment date.

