### 7.2. Demographic and Other Baseline Characteristics

Demographics and baseline characteristics will be summarized for the PNCR dataset and separately for the SS overall and by dose and age group, with descriptive statistics including n, mean, standard deviation, median, minimum, and maximum for numeric variables and frequency and percentage for categorical variables.

The following characteristics will be summarized for the SS:

Demographics include age, gender, ethnicity, race, weight, length and body mass index.

Age (months) = (dose date - date of birth +1)/30

Length (cm) = Length (in inches) \* 2.54

Weight (kg) = Weight (in lbs) \* 0.4536

Race will be summarized as captured in the eCRF. Patients reporting multiple races will be summarized as 'Multiple'.

Baseline disease characteristics include the following:

- Familial history of SMA including affected siblings or parent carriers
- Gestational age at birth
- Length/weight and head circumference at birth
- Hospitalization information from time of birth including number, duration, and reason for hospitalizations including primary ICD-10 codes if available
- Historical ventilatory support, if any
- Historical feeding support, if any

All demographics and baseline characteristics will be listed for the SS.

The following characteristics will be summarized for each of the three PNCR populations being referenced in this study (refer to Section 5.6 of this SAP):

- Age at PNCR entry (months)
- Age (months) at first HFMSE assessment conducted after reaching 24 months of age
- Gender
- Ethnicity
- Race
- Gestational age at birth
- Height (cm) at PNCR entry
- Weight (kg) at PNCR entry

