time variable. Age at baseline will be used as a covariate. The probability of the ability to stand alone over time will be estimated using Kaplan-Meier methods. A Cox regression model will be used to obtain the hazard ratio with 95% CI for AVXS-101 Dose B to the data from PNCR. In this analysis, patients will be censored at the date of their End of Study visit.

All of the efficacy analyses stated above may be repeated using the ECAS as a sensitivity analysis, in the event the ECAS contains a subset of patients of the ITT Set.

If necessary, an additional set of sensitivity analyses may be conducted to include patients who demonstrated the developmental milestone of standing alone (Bayley-III, Gross Motor Subtest #40) which occurred after but within 3 months of the upper bound of the Month 12 visit window (day 374) due to COVID-19 disruptions.

In the first sensitivity analysis, the proportion of patients  $\geq$  6 months and  $<$  24 months of age at time of dosing that achieve the developmental milestone at any post-baseline visit (considering the expanded 3-month window) will be summarized overall and by dose. The corresponding p-value from a Fisher's exact test will be computed for the comparison between AVXS-101 Dose B and PNCR data. The summary and statistical analysis will be conducted using the ITT Set. The difference in the proportions between AVXS-101 and PNCR will be summarized and the exact 95% CIs will be provided accordingly.

In the second sensitivity analysis, the time from dosing to achieving the ability to stand alone will be summarized for patients overall and by dose in the ITT Set. The study day will be used as the time variable. Age at baseline will be used as a covariate. The probability of the ability to stand alone over time will be estimated using Kaplan-Meier methods. A Cox regression model will be used to obtain the hazard ratio with 95% CI for AVXS-101 Dose B and PNCR. In this analysis, patients who demonstrated the developmental milestone within the expanded 3-month window after Month 12 will be censored at the last attended visit prior to when the Month 12 visit was scheduled to occur.

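### SAP 6.2.2 gives PNCR controls two different time origins; coding the enrollment one would tend to raise the supportive Cox hazard ratios for Dose B

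*SAP*

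**What the plan says.** SAP 6.2.2 defines study day separately for PNCR patients. It first fixes the origin: "the date of baseline assessment for the primary endpoint will be considered study day 1". The formula that follows uses another date: the study day of an event "on or after the date of enrollment is defined as event date – enrollment date + 1". The formula for earlier events also subtracts the enrollment date. The key-definitions table (SAP 1.1) defines study day only by first dose, so it does not help for controls.

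Study day matters in the time-to-event analyses. SAP 8.1.1 states "The study day will be used as the time variable", takes age at baseline as covariate, and fits a Cox model for the "hazard ratio with 95% CI for AVXS-101 Dose B to the data from PNCR". SAP 8.2.1 does the same for walking alone in each age group. Both sections repeat the Cox analysis in a COVID-19 sensitivity version.

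Several sections allow the PNCR baseline assessment to fall after enrollment:

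- SAP 6.2.1: "In cases where the baseline visit HFMSE assessment was not completed, the baseline value will be defined as the first non-missing assessment".
- SAP 6.5: a missing baseline is re-mapped to the earliest later assessment. The worked example moves it to Visit Month 4.
- SAP 5.6.1: for the older group, the enrollment visit and the HFMSE baseline taken between 24 and 60 months are described separately.
- SAP 5.6.2: for the Sensitivity PNCR group, baseline is the first visit between ages 2 and 5 years.
- SAP 7.2: age at PNCR entry is tabulated alongside "Age (months) at first HFMSE assessment conducted after reaching 24 months of age".

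**The concern.** The two sentences agree only for controls whose baseline assessment took place on the enrollment date. For the others, the enrollment formula adds the interval between enrollment and baseline to their event or censoring time. Treated patients gain nothing comparable, because their day 1 is the dose date.

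Under the replacement rule, baseline cannot precede enrollment, so control times can only lengthen. Controls then appear to reach milestones later and to stay longer at risk without an event, which generally moves the hazard ratio in favor of AVXS-101. The model would also adjust for age at baseline while counting time from a different date.

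At stake are the reported Cox hazard ratios for standing and walking. A programmer could reasonably code the explicit formula, and the independent programming check in SAP 17 would not reveal the problem if both programmers followed it.

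**Working it through.** **1. The plan's own figures.** The documents give no hazard ratio and no power for the Cox model, so only the planning inputs can be checked. SAP 3.7 claims more than 90% power for standing with 12 Dose B patients, 85% versus 14%, two-sided Fisher test at 0.05. Summing the binomial probabilities of all outcomes with Fisher p ≤ 0.05, for 12 versus 51 (control count from SAP 5.6.1), gives 99.9%. For walking, 60% versus 10%, it gives 94.3%. Both agree with the claim. The re-mapping example in SAP 6.5 also reproduces: visit month minus 4 turns 6, 9 and 12 into 2, 5 and 8.

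**2. One control under each sentence.** Take the SAP 6.5 patient with baseline at Visit Month 4. Assume enrollment at Visit Month 0, 30-day months, and standing first scored at Visit Month 6.

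- Baseline origin: (180 − 120) + 1 = day 61.
- Enrollment origin: (180 − 0) + 1 = day 181.

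The same event moves by 120 days. SAP 8.1.1 also counts a control already standing at Baseline as an achiever; that event would be day 1 under one rule and day 121 under the other.

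**3. Direction.** If every control is shifted by the same gap, at least as many controls are at risk at each treated event, and no more treated patients are at risk at each control event. The unadjusted Cox estimate then cannot fall. With unequal gaps it can fall in a particular data set, so direction was checked by simulation.

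**4. Size.** Inputs from the documents: 12 treated, seen monthly; 51 controls, seen at months 2, 4, 6, 9 and 12 (SAP 5.6); response 85% and 7/51. Assumptions: exponential times; 7/51 read as a 12-month rate, although SAP 5.6.1 gives it no time limit; no age covariate; shifted times not cut off at 12 months; share affected 10% to 100%; gap 2 to 6 months.

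Daily hazard = −ln(1 − p)/360, so the expected ratio is ln(0.15)/ln(1 − 7/51) = 1.897/0.1476 ≈ 12.9 (12.6 with 14%). About 400 data sets per setting were each fitted twice, once with each origin. Median hazard ratios for a four-month gap:

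| Controls affected | Baseline origin | Enrollment origin | Ratio |
|---|---|---|---|
| 10% | 12.98 | 13.81 | 1.06 |
| 25% | 13.19 | 14.89 | 1.13 |
| 50% | 13.13 | 18.04 | 1.37 |
| 100% | 12.73 | 25.78 | 2.03 |

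The baseline-origin column varies only through simulation error. Over all gaps tried, the smallest change was 12.88 to 13.30 (10% affected, 2 months) and the largest 13.87 to 33.81 (100%, 6 months).

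With no true effect (13.7% in both groups) and a four-month gap, the median went from 1.17 to 1.27 at 10%, 1.05 to 1.18 at 25%, 1.23 to 1.68 at 50%, and 1.12 to 2.25 at 100%. Simulation used only runs with events in both groups, 312 to 351 per setting in this null case. Across all settings, including an intermediate 30% treated response, the hazard ratio fell in 0% to 15% of runs.

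**The case against.** The strongest reply is that the bias is conditional. The first sentence of the PNCR definition sets the right origin as plainly as the formula sets another. Nothing shifts unless the formula is coded over that sentence and a control's two dates differ. SAP 5.6.1 equates enrollment with the baseline visit, so the dates coincide for any control assessed on HFMSE at that visit. This stands: a reader might infer that the hazard ratio is biased as planned, and the documents do not show that.

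A reader might also infer gaps of a year or more, because HFMSE is intended from 24 months of age and some controls may have enrolled younger. The 24-month start is a rule for this trial's schedule. Nothing says that PNCR withheld HFMSE before that age, and the SAP 7.2 item does not exclude earlier assessments. The only re-mapping gap the documents illustrate is four months.

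The reach is limited too. Time to standing supports the primary analysis, and time to walking is additional to the secondary one. The Fisher comparisons count milestones in the 12 months from Baseline, and the MMRM uses PNCR visit month (SAP 6.5); neither uses study day. For Kaplan-Meier, SAP 8.1.1 says only "The probability of the ability to stand alone over time will be estimated using Kaplan-Meier methods" and does not name PNCR, and the main walking paragraph has no Kaplan-Meier estimate. Those results are affected only if a PNCR curve is drawn.

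What the reply does not remove is the contradiction in current text, which no other section resolves.

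**Conclusion.** The contradiction is real and should be corrected. Confidence is high that the two origins conflict and that the enrollment formula generally favors AVXS-101 wherever the dates differ. Confidence in the size is low, because the number of controls affected and their gaps are not given. On the assumptions above, a four-month gap raises the median hazard ratio by about 6% if 10% of controls are affected and doubles it if all are.

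The damage is confined to the Cox hazard ratios for standing and walking against PNCR, including the COVID-19 versions. A reader might infer that the trial's main efficacy p-values are at risk. They are not: none of the primary or secondary tests depends on this definition.

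**What to change.** In SAP 6.2.2, replace all four references to enrollment in the two PNCR formulas with the date of the baseline assessment, after any re-mapping under 6.5. Day 1 then means the same in every sentence and matches the 12-month window counted from Baseline in 8.1.1 and 8.2.1.

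Add one sentence giving the PNCR censoring date on that scale; 8.1.1 refers only to the End of Study visit and has no PNCR rule. State whether a PNCR Kaplan-Meier curve will be produced.

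The cost is a few words, one derivation and no new data. SAP 2.2.2 reports that an analysis after the last Cohort 2 visit has already been done, so check which origin was coded there and rerun the Cox models if it was enrollment. Reporting how many controls have a gap, and how long it is, would replace the assumed range with a known figure.

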#### **6.2.3. Dose Date**

The dose date, study day 1, will be the date of administration of the dose of study product.

#### **6.2.4. Final Treatment Value**

The final treatment value for each patient enrolled in the study is the last non-missing measurement collected after study day 1. For the patients from PNCR dataset, the final treatment value is the last non-missing measurement collected after study day 1 and on or prior to visit Month 12.

#### **6.2.5. Final Study Value**

The final study value for each patient enrolled in the study is the last non-missing measurement collected. For patients from PNCR dataset, the final study value is the measurement collected on or prior to visit Month 12.

#### **6.2.6. Age at Baseline**

Age at baseline for patients enrolled in the study is defined as the age at the dose date. Age at baseline for patients from the PNCR dataset is defined as age at baseline. Age will be defined/displayed in months.

### **6.3. Missing Data**

Patients are allowed to withdraw from the study at any time. Analysis of quantitative and categorical variables will include data from patients with non-missing values. For continuous variables, a MMRM model may be used for the comparison between AVXS treated patients and the matching PNCR cohort.

Imputation of missing or incomplete dates will only be performed on AEs and concomitant medications for determining the timing relative to the dose of study product unless otherwise specified. The rules of imputation of missing dates are specified in Table 1 and Table 2. Partial or missing dates will be listed as recorded in the electronic case report form (eCRF). All imputed dates will be no earlier than the patients' birth date.

**Table 1: Rules of Date Imputation: Pre-Dose Assessments**

Partial Missing Start Date	Imputed Start Date
Missing month and day, but the year is present	January 1 of that year or dose date if the year is the same as the year of dose date
Missing day, but year and month are present	First day of that month or dose date if the year and month are the same as the year and month of dose date
Missing month, but year and day are present	Missing month imputed as January

**Table 2: Rules of Date Imputation: Post-Dose Assessments**

Partial Missing Start Date	Imputed Start Date
Missing month and day, but the year is present	Date of dose
Missing day, but year and month are present	First day of that month or dose date if the year and month are the same as the year and month of dose date
Missing month, but year and day are present	Month of dose

## 6.4. Derived and Transformed Data

### 6.4.1. Primary Safety Variables

The primary safety endpoints are defined as follows:

- Any AE
- Any serious AE
- Any AE related to study product
- Any AE with CTCAE Grade  $\geq$  Grade 3

The AEs will be collected from eCRF based on the Schedule of Assessments in SAP Appendix 19.2.

### 6.4.2. Secondary Safety Variable

The secondary safety endpoint is defined as average number of hours per day of non-invasive ventilatory support.

The number of hours per day of non-invasive ventilatory support will be summarized by visit and cohort using descriptive statistics.

### 6.4.3. Primary Efficacy Variables

Bayley-III is a standardized, norm-referenced assessment tool used to identify developmental issues during early childhood. The gross and fine motor subtests will be completed within 30 days of dosing at baseline and then monthly through Month 12. The score of each scale/subtest will be captured in the eCRF. No missing scores will be imputed.

The achievement of significant developmental milestones will be assessed by the CE using a standard Developmental Milestone Checklist shown in Table 3 with definitions of each developmental milestone driven by Bayley-III. Developmental milestones will be assessed by the CE at the investigational site; the physical assessments will be captured on video. Video taken outside of the investigational site (i.e., at the patient's home) which demonstrates the achievement of a developmental milestone is also acceptable. All video evidence of developmental milestone achievement will then be reviewed and confirmed by an independent central reviewer. Aside from analysis of the developmental milestones defined in the primary and secondary efficacy objectives, only descriptive statistics are planned.

**Table 3: Developmental Milestone Checklist**

Developmental Milestone- Bayley Scales Item Number	Performance Criteria
Head Control – Gross Motor Subtest Item #4	Child holds head erect for at least 3 seconds without support
Rolls from Back to Sides – Gross Motor Subtest Item #20	Child turns from back to both right and left sides
Sits Without Support – Gross Motor Subtest Item #26	Child sits alone without support for at least 30 seconds
Stands With Assistance - Gross Motor Subtest Item #33	Child supports own weight for at least 2 seconds
Crawls – Gross Motor Subtest Item #34	Child makes forward progress of at least 5 feet by crawling on hands and knees
Pulls to Stand – Gross Motor Subtest Item #35	Child raises self to standing position using chair or other convenient object for support
Walks With Assistance – Gross Motor Subtest Item #37	Child walks by making coordinated, alternated stepping movements
Stands Alone – Gross Motor Subtest Item #40	Child stands alone for at least 3 seconds after you release his or her hands
Walks Alone – Gross Motor Subtest Item #43	Child takes at least five steps independently, displaying coordination and balance

The primary efficacy endpoint for the patients  $\geq$  6 months and  $<$  24 months at time of dosing is the proportion of patients achieving the ability to stand alone. The ability to stand alone will be evaluated by the CE using the Bayley-III – Gross Motor Subtest # 40 at visits specified by the Schedule of Assessments. Patients who achieve standing alone at any post-procedure visit up to 12 months will be classified as responders. Otherwise, the patient will be classified as a non-responder.

The HFMSE was devised for use in children with SMA Type 2 and Type 3, age 24 months and above, to give objective information on motor ability and clinical progression. The HFMSE will be administered by a CE in accord with the Protocol Schedule of Assessments within 30 days of dosing and monthly through twelve (12) months for all patients  $\geq$  24 months of age. The primary efficacy endpoint for the patients  $\geq$  24 months and  $<$  60 months at time of dosing is the change from baseline in HFMSE. The change from baseline to the 12-month study visit will be calculated.

#### 6.4.4. Secondary Efficacy Variables

The secondary efficacy variable is defined as follows for both patient strata (aged  $\geq$  6 and  $<$  24 months at dosing, aged  $\geq$  24 and  $<$  60 months at dosing):

- Ability to walk alone per Bayley-III Gross Motor Subtest # 43.

For the summary of each age group, the data from the historical dataset of PNCR network will also be included by the matched age group and analysis visits. The PNCR dataset evaluated the ability to walk alone, as per the HFMSE item #20. The HFMSE will not be started until patients reach 24 months of age; however, the Bayley-III will be assessed at Screening and all study visits.

